9. APPENDICES

9.1. Protocol Schedule of Activities

Refer to Protocol Section 1.3 for the Schedule of Activities.

9.2. Changes from Analyses Specified in the Previous Version of the SAP

See [Section 4.2](#) of this SAP.

9.3. Sample Size, Power, and Randomization

A sample size of 243 patients (162 ravulizumab + BSC, 81 BSC alone) is required to ensure at least 90% power and detect an improvement in survival from 60% in the BSC alone group to 80% in the ravulizumab + BSC group at Day 29.

This sample size calculation was performed in EAST 6.5 and assumes:

- 1-sided Z-test of the difference in 2 proportions,
- Type I error = 0.025,
- Pooled variance,
- 2:1 randomization on the 2 treatment groups,
- One interim analysis at 50% information which will be after collecting primary efficacy data on approximately 122 patients. The early stopping boundaries for efficacy and futility (non-binding) will be constructed using α -spending function as Lan-DeMets spending function with O'Brien-Fleming flavor and β -spending function as Gamma(-4) ([Lan, 1983](#); [Hwang, 1990](#)).

Considering a nonevaluable rate of 10%, this study is planned to randomize approximately 270 patients (180 ravulizumab + BSC, 90 BSC alone).

9.4. Technical Specifications for Derived Variables

The following derived data will be calculated prior to analysis. For all dates (except AE and medication dates), in cases where only the month and year are provided for a date, the day for the date will be imputed as 15. Missing month will be imputed as June. In cases where the day is observed but the month is missing, the date will be imputed as June 15.

9.4.1. Age at First Dose

Age at first dose will be calculated as: Year of first dose - Year of birth.

9.4.2. Definition of Baseline Values

Baseline is defined as the last available assessment on or before Day 1 for all patients. Day 1 will be defined as the date of the first infusion of ravulizumab for patients randomized and dosed with ravulizumab and as the later of the date of randomization or the date of Day 1 visit for patients randomized but not dosed with ravulizumab.

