PK/PD/Immunogenicity Tests										
PK 		X	X	X	X	X	X	X		
Total and free C5 		X	X	X	X	X	X	X		
Immunogenicity (predose) 		X					X	X		
Biomarker Tests										
Serum and plasma biomarkers (predose) 	X	X	X	X	X	X	X	X		
Other										
Concomitant medication 	X	<<monitor continuously>>								X
Nonpharmacologic treatments and therapies 	X	<<monitor continuously>>								X
Patient-reported Outcomes										
SF-12							X			X
EQ-5D-5L							X			X

. The Day 1 visit may occur on the same day as Screening.

. Patients randomized to ravulizumab + BSC will receive a weight-based dose of ravulizumab on Day 1 (Table 5). On Day 5 and Day 10, additional doses of 600 mg or 900 mg ravulizumab will be administered (according to weight category) and on Day 15 patients will receive 900 mg of ravulizumab.

. If a patient is discharged before the end of the Primary Evaluation Period (Day 29), the patient will undergo the early discharge assessments. In addition, the patient will be contacted via telephone on Day 29 to assess health status (eg, survival, mechanical ventilation, hospitalization, intensive care unit, and dialysis). Follow-up telephone calls should be performed as planned unless the patient withdraws consent.

. The Early Termination Visit is to be conducted when the patient discontinues from the study during the Primary Evaluation Period. In addition, the patient will be contacted via telephone on Day 29 to assess health status (eg, survival, mechanical ventilation, hospitalization, intensive care unit, and dialysis).

. Additional monitoring will be performed during the 2 follow-up visits to review patient status, including survival and pregnancy, and to obtain information about new or worsening TESAEs. The follow-up will be conducted as a telephone call if the patient is discharged from the hospital or an in-person visit if the patient is still hospitalized.

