6. Confirmation of meningococcal vaccination within the past 5 years prior to dosing for patients randomized to ravulizumab + BSC. If vaccination cannot be confirmed, the patient should receive prophylactic antibiotics prior to initiating ravulizumab treatment and for at least 8 months from the last infusion of ravulizumab. When patients are vaccinated less than 2 weeks prior to treatment with ravulizumab or after initiation of ravulizumab, they should continue antibiotic prophylaxis for at least 2 weeks after meningococcal vaccination.
7. Can be performed within the 3 days prior to Screening or at Screening. Imaging performed as part of the patient's routine clinical care is expected and acceptable for inclusion in this study.
8. Urine or serum pregnancy tests (beta human chorionic gonadotropin) to be performed in all female patients. A negative pregnancy test result is required before administration of ravulizumab.
9. SpO2 to be measured by pulse oximetry. PaO2 to be measured by arterial blood gas, if available. FiO2 to be measured by supplemental oxygen. For patients treated with ravulizumab, SpO2, PaO2 (if available), and FiO2 should be measured predose on Day 1. The highest daily measurement of oxygen pressure or saturation on the lowest inspired supplemental oxygen level will be recorded in the CRF/eCRF.
10. Complete or abbreviated physical examination is to be performed at the timepoints indicated in the SoA. A complete physical examination will include, at a minimum, assessments of the following organs/body systems: skin, head, ears, eyes, nose, throat, neck, lymph nodes, chest, heart, abdomen, extremities, and musculoskeletal. An abbreviated physical examination consists of at least an evaluation of the respiratory and cardiovascular systems. Clinically significant abnormalities or findings will be recorded in the AE CRF/eCRF.
11. Vital sign measurements should include systolic and diastolic BP (millimeters of mercury [mm Hg]), heart rate (beats/minute), respiratory rate (breaths/minute), and temperature (degrees Celsius [°C] or degrees Fahrenheit [°F]). These measurements will be taken predose on dosing days.

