12. When the patient is responsive and capable of understanding, review the Patient Safety Information Card (including discussion of the risks of meningococcal infections) during the hospitalization and at discharge. Upon discharge, patients who received ravulizumab, must carry the Patient Safety Information Card at all times and for at least 8 months after the last infusion of ravulizumab.
13. Clinical safety laboratory measurements will be collected predose on dosing days.
14. Serum samples for PK and immunogenicity analyses will be collected at the timepoints indicated in the SoA for patients randomized to ravulizumab + BSC. On Day 1/dosing days, immunogenicity and PK samples will be collected within 4 hours before the administration of ravulizumab (predose) and PK samples will be collected within 4 hours after the end-of-infusion (postdose). Postdose PK samples must be collected from a separate line or needle stick to the noninfused arm, not from the infusion line. Pharmacokinetic and immunogenicity samples can be collected at any time on nondosing days during the Primary Evaluation Period.
15. Serum samples for total and free C5 analyses will be collected at the timepoints indicated in the SoA for all patients. For patients randomized to ravulizumab + BSC, samples will be collected within 4 hours before the administration of ravulizumab (predose) and within 4 hours after the end-of-infusion (postdose) on dosing days. Postdose samples must be collected from a separate line or needle stick to the noninfused arm, not from the infusion line. Samples can be collected at any time on nondosing days during the Primary Evaluation Period.
16. Serum and plasma biomarker samples for biomarker analyses will be collected for all patients at the timepoints indicated in the SoA and stored at the investigational site prior to analysis by Alexion or designee. Samples will be collected predose (any time before infusion start) for patients who are randomized to the ravulizumab + BSC treatment group.
17. Concomitant medications and nonpharmacologic therapies considered relevant to the treatment of COVID-19 (BSC) or ravulizumab treatment (eg, antimicrobials, antimalarials, antivirals, steroids, and vasopressors) that the patient is receiving, at the time of Screening and for treating TEAEs/TESAEs, will be recorded in the AE CRF/eCRF.

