7.2.4. Other Efficacy Analyses

7.2.4.1. Pharmacokinetic and Pharmacodynamic Analyses

Blood samples will be collected to evaluate ravulizumab concentrations over time. Descriptive statistics of ravulizumab concentration data will be presented for patients randomized and treated with ravulizumab for each scheduled sampling time point.

Blood will also be collected to evaluate total and free C5 concentrations. Descriptive statistics will be presented by treatment group and for each scheduled sampling time point. Total and free C5 concentrations will be evaluated by assessing the absolute values and changes and percentage changes from baseline, as appropriate.

By-patient listings of ravulizumab concentrations, as well as total and free C5 concentrations will be produced.

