9.4.3. Change from Baseline

Change from baseline will be calculated as

Change from baseline = Assessment value – Baseline assessment value.

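### The date-based baseline rule, read literally, takes the postdose Day 1 sample as the C5 baseline in ravulizumab-treated patients

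*SAP*

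**What the plan says.** **Baseline.** SAP 9.4.2: "Baseline is defined as the last available assessment on or before Day 1 for all patients". The same rule stands in Protocol 9.4, in the notes to the protocol's objectives and endpoints tables, and in SAP 7.2 and 7.3.

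**Day 1.** SAP 9.4.2: "Day 1 will be defined as the date of the first infusion of ravulizumab for patients randomized and dosed with ravulizumab". This is a date without a clock time. SAP 4.2 (item 1) records that Day 1 was recently revised for undosed patients to bring the arms closer together. That revision did not deal with time of day.

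**C5 sampling.** Protocol Table 1, footnote 15, says of the active arm: "samples will be collected within 4 hours before the administration of ravulizumab (predose) and within 4 hours after the end-of-infusion (postdose) on dosing days". The C5 row of Table 1 begins at Day 1 and has no Screening entry. The immunogenicity and biomarker rows are labelled predose; the C5 row is not.

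**C5 analysis.** SAP 7.2.4.1: "Total and free C5 concentrations will be evaluated by assessing the absolute values and changes and percentage changes from baseline, as appropriate". Summaries are by treatment group and scheduled sampling time. SAP 9.4.3 gives the formula: "Change from baseline = Assessment value – Baseline assessment value". No C5-specific baseline rule appears anywhere.

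**The concern.** A baseline is meant to describe the patient before treatment. For most measures here the date-based rule does no harm, because the Day 1 assessment is specified as predose; safety laboratory tests and vital signs are examples. C5 differs: it is the change-from-baseline measure with a scheduled draw after the infusion on the same calendar date. A programmer who takes the latest record dated no later than Day 1 will pick up that draw. The drug's early effect is then already inside the baseline and is subtracted out of every later change, in one arm only.

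At stake is the change-from-baseline description of a listed pharmacodynamic endpoint. Protocol 4.3 justifies the early additional doses by the need for complete terminal complement inhibition, so the C5 tables are where a reader will look for evidence that the regimen achieved it. Available pharmacodynamic data also go into the primary analysis package (Protocol 9.4, SAP 7). A table showing roughly no change in treated patients would mislead that reader.

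**Working it through.** The plan states no C5 figure to reproduce, and no alpha, power or event calculation bears on the point. The check applies the rule to the schedule and then compares two baselines.

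**Step 1: which record the rule selects**

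- *Ravulizumab patient, illustrative times:* predose sample at 10:00 on Day 1, postdose sample at 14:00 on Day 1. Both carry the Day 1 date, so the later one is chosen and baseline is postdose.
- *BSC patient:* no infusion and no postdose draw. Baseline is the Day 1 sample, which is untreated.
- *Ravulizumab patient infused late:* predose at 20:00 on Day 1, postdose at 01:00 the next day. Only the predose sample is dated Day 1, so baseline is predose. The same happens if the postdose sample is missing.

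The treated arm would therefore mostly have postdose baselines, with some predose ones mixed in.

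**Step 2: effect on the change**

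Formulas: change = value − baseline (SAP 9.4.3); percentage change = 100 × (value − baseline) / baseline.

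The documents give no C5 concentrations, so the inputs are assumptions: predose 100, and a postdose level of 50, 10, 1 or 0.1 that is held to Day 29.

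| Postdose and Day 29 level | % change, predose baseline | % change, rule read literally |
|---|---|---|
| 50 | 100 × (50 − 100)/100 = -50% | 100 × (50 − 50)/50 = 0% |
| 10 | 100 × (10 − 100)/100 = -90% | 0% |
| 1 | 100 × (1 − 100)/100 = -99% | 0% |
| 0.1 | 100 × (0.1 − 100)/100 = -99.9% | 0% |

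Whatever the depth of suppression, a sustained effect reads as no change.

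**Step 3: small later movements**

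Suppose the level falls from 100 to 1 and later rises to 2.

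- Predose baseline: 100 × (2 − 100)/100 = -98%.
- Rule read literally: 100 × (2 − 1)/1 = +100%.

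The sign reverses, because the denominator is the suppressed value.

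**Step 4: mixed baselines**

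Two treated patients with the same course (100 before, 1 after, 1 at Day 29) get a change of 1 − 1 = 0 if the postdose draw fell on Day 1, and 1 − 100 = -99 if it fell after midnight or was missed. The arm mean would depend partly on the hour of infusion.

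**Step 5: whether another section cures it**

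Protocol 8.9 and SAP 5.3 require the clock time of each sample, so a predose baseline can be derived. Neither says that it must be. Protocol 8.11 and SAP 5.4 also name total and free C5 among the biomarkers, whose Day 1 samples are predose, but neither document says that those samples supply the C5 baseline.

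**The case against.** The strongest reply is that no competent programmer would do this. Change and percentage change apply only as appropriate, clock times are recorded, samples are distinguished as predose and postdose, and the PK/PD Set in SAP 6.4.1 treats postdose results as a category of their own. The intention is clear enough. That is fair as to likelihood, but the written rule still gives the wrong record, and no C5 exception overrides it.

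The second reply concerns consequence, and it stands in full. C5 is descriptive, lies outside the closed testing procedure, and has no planned formal comparison between arms. Absolute concentrations are also reported by scheduled timepoint, including Day 1 predose and postdose, so suppression can be read directly from them. A reader might infer that the pharmacodynamic evidence as a whole is lost or that a between-arm test is invalid; the documents support neither. Nor do they show how total C5 moves after dosing, so its distortion cannot be sized.

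A reader might also extend the point to SpO2/FiO2, fourth in the testing hierarchy, because footnote 9 of Protocol Table 1 says: "The highest daily measurement of oxygen pressure or saturation on the lowest inspired supplemental oxygen level will be recorded in the CRF/eCRF". That best value could postdate the infusion. The extension does not hold. The same footnote asks for a predose reading on Day 1 in treated patients, and the amendment summary gives establishing baseline as the reason. The best-of-day instruction covers both arms, and no figure is given for an oxygenation effect within hours. Restricting only treated patients to the predose pair could itself create bias: one predose reading cannot exceed that patient's best of the day, so treated baselines would tend to be lower while BSC baselines stayed best-of-day.

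**Conclusion.** The point holds for C5. As written, the rule normally assigns a postdose baseline to dosed patients and an untreated one to BSC patients, so the treated arm's change and percentage change from baseline in C5 would be wrong. The 0% against -99% contrast assumes a sustained fall from 100 to 1; across assumed postdose levels from 50 to 0.1, the true fall of 50% to 99.9% reads as 0% each time. Free C5 is the main casualty, because the protocol's rationale expects terminal complement inhibition to be prompt, full and lasting. That rationale describes complement activity rather than a free C5 concentration, so the size remains an assumption.

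Not every dosed patient would be affected: those whose postdose draw is missing or falls on the next date keep a predose baseline. Absolute C5 values, the primary endpoint, the secondary hierarchy, alpha and power are untouched. This is a correction worth making to a descriptive analysis, and it gives no ground for altering the SpO2/FiO2 baseline.

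**What to change.** Add one sentence to SAP 9.4.2 and refer to it from SAP 7.2.4.1: for total and free C5 in patients dosed with ravulizumab, baseline is the last non-missing sample taken before the start date and time of the first infusion; where a time is missing, the scheduled predose label decides. Keep the current rule for undosed patients. Leave the SpO2/FiO2 baseline as it is.

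The cost is one sentence and a small change to the C5 derivation, made before the C5 tables are programmed. Sample times are already recorded, so no new data are needed, and the sample size, testing order and stopping boundaries do not change.

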9.4.3. Change from Baseline

Change from baseline will be calculated as

Change from baseline = Assessment value – Baseline assessment value.

9.4.4. Units Conversion

The amount of supplemental oxygen received (FiO₂) may be recorded in either % or liters/minute (L/min) units. It will be assumed that percentage increases by 4% for every additional liter of oxygen flow administered. Hence, the following conversion to % will be used for L/min:

Liters Per Minute	Percentage
0	21
1	24
2	28
3	32
4	36
5	40
6	44
7	48
8	52
9	56
10	60

PaO₂ maybe recorded in either millimeters of mercury (mmHg) or kilopascal (kPa). The following conversion factor will be used to convert kPa to mmHg: 1 kPa = 7.50062 mmHg

9.4.5. Definition of Durations

9.4.5.1. Number of Days Free of Mechanical Ventilation at Day 29

The number of days free of mechanical ventilation at Day 29 among survivors (ie, the number of days alive and free of mechanical ventilation) will be defined as:

Number of days alive – Number of days on mechanical ventilation, where

- Number of days alive = Earliest of Day 29 Visit Date or Disposition Date (for death) – Date of Day 1 + 1; set to 29 if > 29.

- Number of days on mechanical ventilation = sum of total number of days with mechanical ventilation from Date of Day 1 to Date of Day 29 Visit or Disposition Date (for death) ; set to 29 if > 29.

9.4.5.2. Duration of ICU Stay at Day 29

The duration of ICU stay at Day 29 among survivors (ie, the number of days alive and not in the ICU) will be defined as:

Number of days alive – Number of days in ICU, where

- Number of days alive is as defined in [Section 9.4.5.1](#).
- Number of days in ICU = sum of total number of days in ICU from Date of Day 1 to Earliest of Date of Day 29 Visit or Disposition Date (for death); set to 29 if > 29.

Number of days from first ICU date to Day 1 = Date of Day 1 – Date of first ICU entry; set to zero if negative.

9.4.5.3. Duration of Hospitalization at Day 29

The duration of hospitalization at Day 29 among survivors (ie, the number of days alive and not hospitalized) will be defined as:

Number of days alive – Number of days in hospital, where

- Number of days alive is as defined in [Section 9.4.5.1](#).
- Number of days in hospital = sum of total number of days in hospital from Date of Day 1 to Earliest of Date of Day 29 Visit or Disposition Date (for death); set to 29 if > 29.

Number of days from hospitalization to first dose date = Date of Day 1 – Date of hospitalization.

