### 1.3. Schedule of Activities

**Table 1: Schedule of Activities**

Period	Screening Period	Primary Evaluation Period							Follow-up Period 	
		D1 	D5 	D10 	D15 	D22	D29/ Discharge 	Early Termination 	D60	D90
Study Day (D)	D -3 to D -1									
Study Window (days)	NA	NA	±1	±1	±1	±1	±1		±7	
Eligibility										
Informed consent	X									
Inclusion/exclusion	X									
Medical history 	X									
Demographics	X									
Study Administrative										
Confirmation of vaccination or appropriate antibiotic prophylaxis against N. meningitidis 	X								X	
Screening Laboratory Tests										
Confirmed positive SARS-CoV-2 test	X									
Chest CT or X-ray 	X									
Pregnancy test 	X						X	X		
Randomization										
Randomized to study drug + BSC or BSC alone		X								
Administration of Study Drug										
Ravulizumab 		X	X	X	X					
Efficacy Assessments										
Survival status										X
Mechanical ventilation status	X									
Hospitalization status										
Intensive care unit status										
Dialysis status										
FiO 2 , SpO 2 , PaO 2 										
Sequential Organ Failure Assessment score	X	X	X	X	X	X	X	X	X	
Safety Assessments										
Electrocardiogram	X						X	X		
Complete physical examination 	X						X	X		
Abbreviated physical examination 		X	X	X	X	X				
Glasgow Coma Scale	X	X	X	X	X	X	X	X		

Period	Screening Period	Primary Evaluation Period							Follow-up Period 	
		D1 	D5 	D10 	D15 	D22	D29/ Discharge 	Early Termination 	D60	D90
Study Day (D)	D -3 to D -1									
Study Window (days)	NA	NA	±1	±1	±1	±1	±1			±7
Body weight	X	X	X	X	X					
Vital sign measurements (predose) 	X	X	X	X	X	X	X	X		
Adverse event review and evaluation	X	<<monitor continuously>>								X
Review safety card 		X 					X 	X 		X 
Safety Laboratory Tests (Predose)										
Clinical chemistry	X	X	X	X	X	X	X	X		
Hematology	X	X	X	X	X	X	X	X		
Coagulation panel and D-dimer	X	X	X	X	X	X	X	X		
Urinalysis	X	X	X	X	X	X	X	X		
Direct Coombs test	X									

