5.1.2.1. Mechanical Ventilation

The number of days free of mechanical ventilation is defined as the total number of days from Day 1 to Day 29 without invasive or non-invasive mechanical ventilation.

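### SAP 9.4.5 counts free days to the Day 29 visit date instead of study Day 29, an error of at most one day per patient, and does not say which date applies after early discharge

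*SAP*

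**What the plan says.** SAP 5.1.2.1 defines the first-ranked secondary endpoint over a fixed period, as the "total number of days from Day 1 to Day 29 without invasive or non-invasive mechanical ventilation". SAP 5.1.2.3 and 5.1.2.5 use the same Day 1 to Day 29 period for ICU and hospital stay.

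The derivation in SAP 9.4.5.1 is tied to a visit. It states "Number of days alive = Earliest of Day 29 Visit Date or Disposition Date (for death"), minus the Day 1 date plus 1, set to 29 if larger. Nothing brings an earlier visit up to 29. Days on ventilation are the "sum of total number of days with mechanical ventilation from Date of Day 1 to Date of Day 29 Visit or Disposition Date (for death"), with a cap of 29 on the total only. The ICU and hospital derivations repeat "Number of days alive is as defined in" Section 9.4.5.1 and also sum support days to the Day 29 visit or death.

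In the protocol's Schedule of Activities the last visit of the Primary Evaluation Period is headed "D29/ Discharge", with a window of ±1 day. For a patient discharged before Day 29, footnote 3 says that "the patient will undergo the early discharge assessments. In addition, the patient will be contacted via telephone on Day 29 to assess health status". The status items listed include survival, ventilation, hospitalization and ICU. Protocol 8.4.10 repeats the call. Neither document says which of these two dates is the Day 29 visit date in the SAP formula.

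**The concern.** A free-day endpoint is a count over a fixed horizon. If the horizon moves with the visit date, two patients with the same clinical course can score differently because of scheduling alone.

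There are two sources of movement. One is the visit window, which acts on the formula as written. The other is the unstated date for patients discharged early, which matters only if a programmer takes the discharge record as the Day 29 visit.

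The count feeds ranks 1, 2 and 5 of the testing order in SAP 7.2.2. Rank 1 is the gate: if it fails, no lower-ranked endpoint can be declared significant. The trial is open-label, so a choice of date made after data have been seen would be awkward to defend.

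**Working it through.** **Plan's own figures.** The documents give no expected value, variance or power for the free-day endpoints, so there is no figure to reproduce for them. The sample size concerns the primary endpoint only. A fixed-design calculation for 60% vs 80%, one-sided 0.025, 2:1, pooled variance gives 80 + 160 = 240, against 243 stated. Power at 81 and 162 is 0.904, and 243/0.9 = 270. None of this uses the free-day counts.

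**Formulas.** Let v be the study day of the Day 29 visit for a survivor.
- SAP 9.4.5.1: score = min(v, 29) − min(support days from Day 1 to v, 29).
- Fixed period (SAP 5.1.2.1): score = 29 − support days within Days 1 to 29.

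**Effect of the window (v = 28, 29 or 30).** The patient courses are illustrative.

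| Ventilated on | v | SAP 9.4.5.1 | Fixed period |
|---|---|---|---|
| Days 1–8 | 28 | 28 − 8 = 20 | 29 − 8 = 21 |
| Days 1–8 | 29 | 29 − 8 = 21 | 21 |
| Days 1–8 | 30 | 29 − 8 = 21 | 21 |
| Days 20–30 | 30 | 29 − 11 = 18 | 29 − 10 = 19 |
| Days 1–8 and 20–30 | 30 | 29 − 19 = 10 | 29 − 18 = 11 |
| Days 1–30 | 30 | 29 − 29 = 0 | 0 |

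The fifth row is included because inclusion criterion 4 requires ventilation at entry; the earlier spell lowers both scores equally. The last row shows that the cap on total support days hides the error when support is continuous. A Day 28 visit therefore costs one day if Day 29 is a free day. A Day 30 visit costs one day if the patient is on support on Day 30 and had at least one free day earlier. Otherwise the loss is zero.

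Both errors lower the score. If a share s of an arm is affected, that arm's mean falls by s × 1 day, and the difference between arms shifts by the difference of the two shares. Equal shares cancel. The documents give no visit-timing data, so the shares are unknown.

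**Effect of the date used after early discharge.** Let d be the discharge day and b the support days up to discharge, with none afterwards.
- Telephone contact on Day 29 as the visit date: 29 − b, no loss.
- Discharge date as the visit date: d − b, a loss of (29 − b) − (d − b) = 29 − d.

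For b = 8 and d = 12 the score is 21 with the contact and 12 − 8 = 4 with the discharge date. The loss under the discharge date is 19 days for d = 10, 17 for d = 12, 14 for d = 15, 9 for d = 20 and 4 for d = 25. Hospital-free days for one continuous stay, with the discharge day counted as a hospital day, become d − d = 0 instead of 29 − d (0 instead of 17 for d = 12).

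**The case against.** The best defence is that the horizon is fixed everywhere else and the formula should be read in that light. SAP 5.1.2 uses Day 1 to Day 29, the sensitivity analyses in SAP 7.2.2.1 treat unobserved days as missing up to Day 29, and SAP 9.5.1 censors survival at no later than 29 days. The window is the same in both arms, no difference in visit timing is shown, and one day on a 29-day scale is small. For discharged patients the call is specified for Day 29 itself. All of this stands as to size. It does not repair the formula: a programmer will code SAP 9.4.5.1, which ends at a visit date with a cap and no floor.

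A reader might go further. Because the visit column is shared with discharge, one could infer that a Day 12 discharge stops the count at 12, so that faster recovery scores worse. A patient ventilated for 8 days and discharged on Day 12 would score 4, while one ventilated for 15 days and discharged on Day 25 would score 25 − 15 = 10; the fixed count gives 21 and 14. The documents do not support this as what the plan specifies:
- A shared column header lists assessments; it is not a rule for recording dates.
- Footnote 3 and Protocol 8.4.10 provide a separate Day 29 contact covering the inputs to these endpoints.
- Where the SAP means discharge as an alternative to Day 29, as for SF-12 and EQ-5D-5L, it says so. SAP 9.4.5 does not.
- The discharge reading would give zero hospital-free days to every patient with a single stay discharged before Day 29, which would empty an endpoint that SAP 4.1 describes as days alive and not hospitalized.

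What remains is that the SAP never names the contact as the source of the date.

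**Conclusion.** The derivation in SAP 9.4.5 does not match the fixed-period definitions in SAP 5.1.2. Under the formula as written the error is at most 1 day per patient, always downward, and it needs only the ±1 day window to arise. Its effect on the treatment comparison depends on how far the affected shares differ between arms, which the documents cannot show; there is no evidence of a differential effect.

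Separately, the date for patients discharged early is unspecified. Under the more plausible reading, the Day 29 telephone contact, nothing is lost beyond the window. The large losses in the working, and any reversal of ranking or penalty on an effective drug, hold only if the discharge date is used. They rest on assumed patient courses, since the documents give no distribution of discharge or ventilation times.

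The point touches the secondary endpoints ranked 1, 2 and 5. The primary endpoint, its test and N = 243 are unaffected. It is a small correction, worth making before database lock.

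**What to change.** In SAP 9.4.5.1, and by reference in 9.4.5.2 and 9.4.5.3:

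1. Define days alive as min(death date, Day 1 date + 28) − Day 1 date + 1, set to 29 for every patient known to be alive at Day 29, whatever the visit date.
2. Count ventilation, ICU and hospital days only from the Day 1 date to the Day 1 date + 28.
3. State that, after early discharge, the Day 29 telephone contact establishes status at Day 29, and that the discharge visit is not the Day 29 visit for these derivations.
4. Leave patients whose status is unknown after their last contact to the multiple imputation already specified in SAP 7.2.2.1.

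The cost is a revised formula and two sentences in the SAP, with no new visit and no change to the sample size. One item should be checked: the protocol describes the Day 29 call as a health-status assessment and does not say that it yields dates of any readmission or renewed ventilation since discharge. If it does not, the SAP should state how those days are handled.
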